
### 11.3.1 Efficacy and Safety Monitoring

$R,E$  is the probability of response with the study regimen and its assumed prior distribution is  $\text{beta}(1.6, 0.4)$ .  $R,S$  is the targeted response rate and its assumed prior distribution is  $\text{beta}(80, 20)$ . The trial will be stopped early if  $\text{Pr}[R,E < R,S \mid \text{data}] > 0.95$ .  $T,E$  is the probability of severe toxicity from the study regimen and  $T,S$  is the targeted rate of severe toxicity. The assumed prior distribution of  $T,E$  is  $\text{beta}(0.4, 1.6)$  and the assumed prior distribution of  $T,S$  is  $\text{beta}(20, 80)$ . The trial will be stopped early if  $\text{Pr}[T,E > T,S \mid \text{data}] > 0.925$ .

The stopping boundaries corresponding to above probability criteria are:

Number of Patients Evaluated	Number of Responses <=	Number of Toxicities >=
10	5	5
15	8	6
20	12	8
25	15	9
30	19	11
35	22	12
40	26	13
45	30	15
50	33	16
55	37	17
60	40	19

### 11.3.3 Operating Characteristics

The following table summarizes the probability of stopping early, the expected study size, number of responses, and number of toxicities for the indicated true response and toxicity probabilities:

True Respor Probability	True Toxicit Probability	Probability t trial stops ea	Average Nu of Patients	Average Nu of Responses	Average Nu of Toxicities
0.65	0.10	0.78	31.8	20.7	3.2
0.65	0.20	0.81	30.0	19.5	6.0
0.65	0.30	0.92	23.4	15.2	7.0
0.80	0.10	0.08	56.7	45.4	5.7
0.80	0.20	0.19	52.6	42.0	10.5
0.80	0.30	0.66	36.4	29.1	10.9
0.95	0.10	0.003	59.8	56.8	6.0
0.95	0.20	0.12	55.4	52.6	11.1
0.95	0.30	0.63	38.0	36.1	11.4

At the end of the study, we will estimate the posterior distribution of the response rate and severe toxicity rate. If the trial is not stopped early and 54 responses are observed, the 95% posterior credible interval for response will be 81.1%, 95.9%. If the trial is not stopped early and 5 patients experience severe toxicity, the 95% posterior credible interval for severe toxicity will be 3.1%, 16.8%.

The primary translational endpoint of this study is the change in the stem cell population as measured by flow cytometry from before to after radiation treatment. The change in each measured biomarker will be summarized with standard descriptive statistics such as mean, median, standard deviation, and range. We will determine the association between biomarkers and the change in biomarkers with tumour response and CTC status (present/absent) with a t-test or Wilcoxon's rank sum test as appropriate. All analyses will be repeated in the subgroup of patients diagnosed with inflammatory breast cancer (IBC).

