#### iii. Biomarker Research

The biomarker research objectives of the study are:

- To determine if change in the absolute number of circulating tumor cells (CTCs) in the blood during pre-operative radiation with chemotherapy predicts for percentage of viable cells in a tumor core biopsy expressing putative stem/progenitor cell markers. (Patients whose gross disease cannot be completely encompassed by a combination of locoregional therapy with chemo/HOU/UTMDACCiation and surgery will be analyzed separately).
- To identify tumor and serum biomarkers present at baseline that could be predictive of cCR or benefit of radiation. These will be examined in IBC vs. non-IBC samples.

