### **5.3 CTCs as surrogate cancer stem cell markers**

The field of solid tumor stem cell biology has re-emerged at the forefront of clinical oncology in recent years due largely to the identification of new, prospectively identified stem/progenitor cell markers. Numerous putative markers are currently under investigation and considerable work is being done to identify new ones. This process is beset by two main challenges: how robust are the criteria used to validate the identified cell as a stem cell, and to what degree, under what conditions, and in which patients are identification of these cells reproducible? Thus far, prevailing observations across disease sites are that cancer stem cells are often basal cells, devoid of markers of differentiation such as hormone receptors, and can exhibit similar adhesion molecule profiles, CD44+, and more recently ALDH1. Commonalities among tumor-initiating cell surface markers have facilitated tumor-initiating cell identification in multiple tumor sites; however, the impact of tissue digestion on marker specificity inhibits the use of established cell surface stem cell markers on intact tissue sections or archived tissue. Cell surface molecules while ideal targets for FACS analysis, may not provide the optimal targets for IHC which are critical to widespread biomarker use.

[figure not shown]
The circulating tumor cell (CTC) population is an appealing cancer stem cell surrogate as these cells need not be subjected to digestion for evaluation, and appear to express the markers representative of tumor initiating cells (Figure 3, unpublished data; ARC-MD), hypothetically because they are indeed seeking a niche in which to sustain new disease foci. Prior and ongoing studies have established the feasibility of collecting CTCs in the randomized trial setting, and technology is emerging to facilitate systematic examination and quantitation of these cells. Recently, the U.S. Food and Drug Administration (FDA) approved an assay for the detection of circulating tumor cells in peripheral blood using a semi-automated system, the CellSearch system, and other approaches not yet approved by the FDA are under investigation.

The translational component of this study will correlate the change in CTCs with chemo-radiation treatment to change in expression the best putative stem/progenitor markers on digested tumor tissue. This will assess number of CTCs as a surrogate

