Linear accelerator based CT imaging (CT on rails or cone beam CT) or re-CT-simulation will be performed after 45 Gy to assess for the need to re-plan secondary to response. Tumor size will be documented using recist criteria based on these images. Additional accelerator based CT imaging is acceptable as clinically indicated.

Definitive or palliative local therapy with surgery when indicated will be performed after completion of the combined regimens. If the patient is deemed operable the first follow-up visit will occur after surgery. If the patient is deemed inoperable the first follow-up visit will occur after concurrent Capecitabine and radiation therapy. Subjects will be followed every 3 months (+/- 1 month) post treatment times 1, then every 6 months (+/- 1 months) times 1, then every 12 months (+/- 2 month) times 2. PET/CT scan or ultrasound will be performed in conjunction with the first follow up visit. For patients treated to definitive dose for gross unresected disease (any treatment field receiving a total of > 60 Gy in the mosaic prescription), all sites receiving > 60 Gy will be scored as complete response, partial response, noresponse/progressive disease based on imaging and exam after this visit and when evaluable and all subsequent visits. Subsequent radiologic studies will be at the discretion of the treating oncologist as dictated by standard of care. Toxicity will be recorded at each visit using the RTOG criteria.

Capecitabine dose reduction criteria are as follows:

Capecitabine will be held for patients experiencing grade 3-4 Capecitabine related

toxicities until symptomatic improvement (Grade 1). Radiation therapy will not be held for Capecitabine related toxicities. Patients will then be restarted with reduced dose of Capecitabine (level-1). Level -1 (25% dose reduction) = 600 mg/m^2 BID. If patients develop additional grade 3-4 toxicity in spite of dose reduction, the chemotherapy will be permanently discontinued.

Correlation will be made between Change in CTC level and change in percent of CD44+CD24lo or ALDH1+ cells in the tumor biopsy. Change will be correlated with clinical and pathologic response (in patients who undergo surgery)

Approximately 60 subjects will be enrolled. Assuming an average accrual rate of 3-4 subjects per month, the duration of accrual will be approximately 20 to 26 months.

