## **iii. Translational endpoint:**

The biomarker research objectives of the study are:

- To determine if change in the absolute number of circulating tumor cells (CTCs) in the blood during pre-operative radiation with or without chemotherapy correlates to the percentage of viable cells in a tumor core biopsy expressing putative stem/progenitor cell markers pre and post therapy. Patients whose gross disease cannot be completely encompassed by a combination of locoregional therapy with chemo/HOU/UTMDACCiation and surgery will be analyzed separately.

The Time and Events Table is included in Appendix E.

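### The translational objective is a change-versus-change question on CTC counts, but Section 11.3.3 names another primary translational endpoint and tests CTCs only as present/absent

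*Combined protocol and SAP*

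**What the plan says.** **The question.** Section 1.0 iii asks whether "change in the absolute number of circulating tumor cells (CTCs) in the blood during pre-operative radiation with chemotherapy predicts for percentage of viable cells" with stem/progenitor markers. Section 10.0 iii opens with "To determine if change in the absolute number of circulating tumor cells (CTCs) in the blood" and asks whether that change "correlates to the percentage of viable cells in a tumor core biopsy expressing putative stem/progenitor cell markers pre and post therapy". Both sections want patients whose disease cannot be encompassed by locoregional therapy analysed separately.

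**The intended analysis.** Section 5.3: "The translational component of this study will correlate the change in CTCs" with the change in marker expression on digested tumour. Section 6.0: "Correlation will be made between Change in CTC level and change in percent of" CD44+CD24lo or ALDH1+ cells in the biopsy. Section 2.0 describes the same comparison as an important translational endpoint.

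**The statistical section.** Section 11.3.3: "The primary translational endpoint of this study is the change in the stem cell population as measured by flow cytometry from before to after radiation". Changes get descriptive summaries. Biomarkers and their changes are then related to tumour response and to "CTC status (present/absent) with a t-test or Wilcoxon's rank sum test as appropriate", with a repeat in the IBC subgroup.

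**The analysis set.** Section 11.6 restricts the primary translational analysis to patients with both biopsies. Section 5.3 makes participation optional.

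**The concern.** The objective relates two quantitative measures, one of them a change in a count. Section 11.3.3 puts only the stem-cell measure into the primary translational endpoint and uses CTC as a two-level grouping factor. It does not say whether the status is taken before treatment, after it, or at both times. It names no correlation or regression method, significance level or power.

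Three things are at stake:

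- The paired biopsies and blood draws are taken to answer this question, and the written tests do not answer it.
- With two endpoints and two analyses in one document, the choice between them could be made after the data are seen.
- Section 2.0 foresees asking for more accrual if translational power is inadequate. That power cannot be calculated until the plan settles which endpoint and which test are meant.

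**Working it through.** **1. The plan's own figures.** None is given for the translational analysis. The two credible intervals in the same section reproduce: Beta(1.6+54, 0.4+6) gives 81.1% to 95.9%, and Beta(0.4+5, 1.6+55) gives 3.1% to 16.8%. The response and toxicity arithmetic is not in question.

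**2. The sections side by side.**

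| Section | CTC variable | Marker variable | Method |
|---|---|---|---|
| 1.0 iii | change in absolute number | percentage | predicts; no test |
| 10.0 iii | change in absolute number | percentage, pre and post | correlates; no test |
| 5.3 | change | change in expression | correlate; no test |
| 6.0 | change in level | change in percent | correlation; no test |
| 11.3.3 | present/absent, time not stated | change (primary), level | t-test or Wilcoxon |

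The only row with a named test is the only row without CTC change. The other four rows also differ on the marker variable.

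**3. Cost of splitting CTC, treated as one variable.** The documents give no correlation and no number of pairs. Assumed: correlation 0.4, 40 pairs (the ceiling is the 60 enrolled), two-sided 5%. Section 5.2 says CTCs are found in up to 30% of patients without known metastases. The trial also admits oligometastatic patients, so 30% and 50% present are both shown.

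*Formula, continuous and untied CTC.* Splitting a normal variable with fraction p present multiplies the correlation by φ(z_p)/√(p(1−p)). This is 0.759 at p = 0.3 and 0.798 at p = 0.5. Power is approximately Φ(atanh(r)·√(n−3) − 1.96).
- Unsplit: atanh(0.4) = 0.424; 0.424 × √37 = 2.58; Φ(0.62) = 0.73.
- Split at 30%: r = 0.4 × 0.759 = 0.303; atanh = 0.313; 0.313 × √37 = 1.91; Φ(−0.05) = 0.48.

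*Simulation, 40 pairs.* In the zero-heavy rows, absent means a count of zero, and positive counts are skewed and rounded up.

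| CTC data | Spearman | Wilcoxon on present/absent | Gap (points) |
|---|---|---|---|
| Continuous, untied, split at 30% or 50% | 0.69–0.70 | 0.47–0.51 | about 20 |
| 50% zero | 0.60 | 0.50 | about 10 |
| 70% zero | 0.51–0.52 | 0.46–0.47 | about 4 to 5 |

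Most of the gap in the first row comes from assuming no ties.

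**4. Status against change.** Step 3 compares one variable before and after splitting. It does not measure the actual mismatch, which is status in Section 11 against change in the objective. A separate assumed model used skewed, zero-heavy counts before and after treatment, with marker change following CTC change (latent correlation 0.6, 60 pairs):

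| Patients with possible CTCs | Spearman on change | Baseline status | Post-treatment status |
|---|---|---|---|
| 50% | 0.42 | 0.05 | 0.09 |
| 30% | 0.25 | 0.05 | 0.07 |

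Other settings of such a model gave 0.32 to 0.53 for Spearman and about 0.05 to 0.07 for status. Baseline status has power near the 5% error rate because, in this model, it carries almost no information on change.

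**The case against.** **The correlation is already in the protocol.** Sections 5.3 and 6.0 state it, and nothing says Section 11 overrides them. Section 11 can be read as adding to them. This stands as far as it goes: a reader might infer that the plan drops the CTC-change analysis or that Section 11 governs, and the documents support neither. But Section 6.0 gives no method, significance level or precision, and Section 11 does not carry the correlation forward.

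**Present/absent is defensible with sparse counts.** Section 5.2 itself describes CTCs by detection and by a threshold. This also stands. A reader might infer that splitting the count wastes some 20 points of power. That requires continuous, untied counts, which is hard to square with the up-to-30% detection figure. The criticism that survives is that a status is not a change.

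**Change in biomarkers in 11.3.3 might include CTCs.** Even so, that change would be related only to response and to CTC status, never to marker percentage.

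**The component is optional and hypothesis-generating.** True, and it limits the weight of the point.

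**Conclusion.** The plan is inconsistent on its translational endpoint and analysis, and the only tests named in Section 11 do not address the question that Sections 1.0, 5.3, 6.0 and 10.0 pose. That conclusion comes from the text and needs no simulation.

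The size cannot be settled from the documents. Treating CTC as one variable (assumed correlation 0.4, 40 pairs), the cost of splitting is about 4 to 5 points at 70% zeros, about 10 at 50% zeros, and about 20 only without ties. For an association with change itself, baseline status had power near the error rate under one assumed pre/post model. If baseline status and CTC change were related, it would do better.

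This concerns an optional translational objective. It should not be read as a flaw in the response analysis, the toxicity monitoring or the stopping boundaries, none of which uses CTC data.

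**What to change.** In Section 11.3.3:

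- Align the primary translational endpoint with Sections 1.0, 6.0 and 10.0, and settle on one marker variable among percentage, pre and post percentages, and change. Use the same wording in all sections.
- Prespecify, in patients with paired biopsies, a tie-corrected Spearman correlation with 95% CI between change in CTC count and change in percent marker-positive cells.
- State how patients with zero CTCs at both times are handled.
- Report separately the patients whose disease cannot be encompassed by locoregional therapy, as Sections 1.0 and 10.0 require.
- Keep CTC present/absent, with its time point stated, and the plain change in stem cells as supporting analyses.
- State the expected number of pairs and the precision or detectable correlation, so that the accrual provision in Section 2.0 has something to refer to.

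The cost is wording. Section 5.2 says the assay quantitates CTCs, and no new samples, assays or visits are needed.

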#### **11.4 Sample Size Re-estimation**

Sample size re-estimation is not planned for this study.

#### **11.5 Analysis Populations**

Analyses of both efficacy and safety will be performed in the intent-to-treat (ITT) population, and will comprise all patients who received at least one dose of the investigational product. The surgical population includes only subjects who underwent definitive surgery.

#### **11.6 Efficacy Analysis**

The ITT population will be used for the primary analysis of both the efficacy and safety data. The surgical population will be used for a secondary analysis of the surgical efficacy data. Only patients who undergo both pre-treatment and post-treatment core biopsies will be considered in the primary translational analysis.

##### **11.6.1 Primary Analysis**

The primary endpoint in this study is response defined as the percentage of subjects achieving a complete or partial tumor response using RECIST criteria. The response rate will be calculated from the view of best response that records confirmed cases of CR or PR. Subjects with unknown or missing response will be treated as non-responders; i.e., they will be included in the denominator when calculating the percentage. Response will be evaluated by the recist criteria 4 weeks (+/- 4 days) after completion of radiation therapy.

##### **11.6.2 Secondary Analysis**

Patients who were deemed at time of enrolment to be inoperable or questionably inoperable (requiring flap closure with doubt regarding ability to obtain negative margins based on surgical oncology assessment) who have objective clinical response and receive mastectomy or are offered mastectomy but refuse will be considered having converted to operable. Patients who are resectable but considered inoperable based on advanced locoregional disease or M1 disease who have a mastectomy and no FDG-avid disease on PET at 3 month follow up will also be considered having converted to operable.

A secondary indicator of treatment efficacy is pCR. pCR is defined as the lack of any invasive disease in the breast and lymph nodes. A pathologist at the University of Texas M.D. Anderson Cancer Center will perform accurate sampling and review of all cases that have surgery. pCR will be assessed at the time of surgery following the completion of all protocol specified neoadjuvant chemotherapy, which will be approximately 26

weeks following the start of neoadjuvant chemotherapy. Subjects with unknown or missing response and those who do not convert to operable will be included in the primary efficacy analysis as non-responders.

A secondary analysis will calculate response rate based on subjects with evaluable tumor response only; i.e., the denominator will only include subjects with CR, PR, SD, or PD and will not include those with unknown or missing best response.

Exact 95% confidence limits for the clinical response rate will be calculated.

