#### i. Efficacy

The secondary efficacy objectives of the study are:

- To determine the rate of conversion to operable, cCR, and pCR after completion of all protocol specified therapy. This includes the following:
  - Pre-operative concurrent radiation with capecitabine to the breast and at risk or involved regional lymph node basins
- To determine locoregional control of unresected nodal disease treated to definitive radiation dose ( $\geq 60\text{Gy}$ )

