## 8.0 Selection of Patients

### 1. 8.1 Inclusion Criteria

1. Histological confirmation of invasive breast cancer
2. No contraindications to receiving a course of radiation treatment (pregnancy, prior radiation to the volume with disease, or systemic disease in which radiation therapy is an absolute contraindication).
3. Patients who have chemo-refractory gross disease in the breast causing symptoms (pain, drainage, duress) OR

gross disease in the breast ( $\geq T3$ ) and/or lymph node(s) progressive, persistent, or minimally responsive to chemotherapy deemed inoperable or questionable inoperable  
OR

recurrent gross disease in a previously unirradiated breast or on the chest wall or in the regional lymphatics (core biopsy will not be offered to patients without gross disease in the breast).

4. Are able to swallow and retain oral medication (intact pill).
5. Age over 18.
6. Female gender

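### Conversion to operable credits only mastectomy, so a resected recurrence in a patient with no remaining breast cannot count, and its second route depends on a PET that the protocol does not require

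*Combined protocol and SAP*

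**What the plan says.** The secondary efficacy objectives in section 1.0 open with conversion: "To determine the rate of conversion to operable, cCR, and pCR after completion of all protocol specified therapy". Section 11.6.2 defines it by two routes.

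- **First route.** Patients inoperable or questionably inoperable at enrolment "who have objective clinical response and receive mastectomy or are offered mastectomy but refuse will be considered having converted to operable". There is no PET condition.
- **Second route.** This covers "Patients who are resectable but considered inoperable based on advanced locoregional disease or M1 disease" and counts those "who have a mastectomy and no FDG-avid disease on PET at 3 month follow up will also be considered having converted to operable". It has no response condition, no credit for refusal, and no anatomical limit on the FDG finding.

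On imaging, section 6.0 says "PET/CT scan or ultrasound will be performed in conjunction with the first follow up visit". After that visit, "Subsequent radiologic studies will be at the discretion of the treating oncologist as dictated by standard of care".

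On eligibility, section 8.1 admits "recurrent gross disease in a previously unirradiated breast or on the chest wall or in the regional lymphatics", and the same criterion recognises that some patients have no gross disease in the breast. Section 6.0 likewise lists breast, chest wall and lymph nodes as sites of gross disease, and admits oligometastatic patients.

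Section 10.0 restates the objective but adds a limit to patients who go on to surgery. Section 1.0 has no such limit.

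**The concern.** The endpoint is meant to show how often chemoradiation makes inoperable disease operable. The scoring rule is narrower than the population enrolled: it recognises one operation, which a patient without a breast cannot have. For one group it also relies on a scan that the visit schedule leaves optional. The reported rate could then depend partly on how many recurrences were enrolled and on which imaging was ordered, as well as on the effect of treatment. Operability is central to the rationale in section 2.0, so readers will look for this rate.

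**Working it through.** **Plan's own figure.** None exists. The documents give no target, power or precision for conversion, so the check sets the rule against the eligible population and the visit schedule.

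**Step 1. Apply each route to the patients who may be enrolled.**

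| Patient | First route | Second route |
|---|---|---|
| Breast in place, objective response, mastectomy done or offered and refused | Converted | – |
| Breast in place, resectable but considered inoperable, mastectomy, PET clear | – | Converted |
| As the row above, but ultrasound only | – | No FDG reading; cannot be shown to meet the rule |
| As the second row, but distant FDG-avid disease on PET | – | Not converted, whatever the locoregional result |
| Breast already removed, inoperable chest-wall or nodal recurrence, later resected | Not converted | Not converted |

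**Step 2. Is the last row real?** Section 8.1 admits chest-wall and regional nodal recurrence, and section 2.0 describes recurrence after definitive therapy. That some of these patients have had a mastectomy is an inference. Prior radiation to the diseased volume is excluded, which narrows the group, and a nodal recurrence can occur with the breast intact. No count is given.

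**Step 3. Is the missing PET real?** The first follow-up falls 3 months (± 1 month) after treatment, which matches the 3-month PET in 11.6.2. Ultrasound alone satisfies 6.0 at that visit, and later imaging is discretionary. The missing-data wording in 11.6.1 and 11.6.2 concerns response, not conversion.

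**Step 4. Denominator.** Under section 10.0's surgery-only limit, an unoperated recurrence drops out, but a resected one went to surgery and remains as a failure. The same limit conflicts with the first route, which credits patients who refuse the operation and so would not be in that denominator. An all-treated denominator has the opposite problem: section 8.1 admits symptomatic or recurrent disease without requiring that it was judged inoperable, and such patients have nothing to convert from.

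**Step 5. Illustrative size.** Assume all N = 60 (section 11.3) are the denominator, a share u cannot qualify, and the rest convert at rate c.

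Highest reachable rate = 1 − u. Observed rate = (1 − u) × c. For c, use 91% (the 55-patient retrospective review) and 23/28 = 82.1% (the 28-patient phase II study), both in section 3.5.

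| u (assumed) | Ceiling | c = 91% | c = 82.1% |
|---|---|---|---|
| 0% | 60/60 = 100% | 91.0% | 82.1% |
| 10% | 54/60 = 90% | 81.9% | 73.9% |
| 20% | 48/60 = 80% | 72.8% | 65.7% |
| 30% | 42/60 = 70% | 63.7% | 57.5% |

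If the denominator is operated patients, the ceiling is 1 − v, where v is the share of operated patients whose resection was not a mastectomy or who lack the PET under the second route. The documents give neither u nor v.

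**The case against.** Four points carry weight.

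First, the gap is narrower than a quick reading of 11.6.2 suggests. A reader might infer that anyone imaged by ultrasound cannot convert, or that distant disease decides the result in M1 patients. Neither follows. The first route has no PET condition. In the second, distant disease is a veto on top of the mastectomy requirement. An M1 patient who was inoperable at enrolment might fall under the first route, since the plan states no precedence.

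Second, the FDG condition has a coherent purpose. M1 disease is itself a second-route reason for being considered inoperable, so asking whether FDG-avid disease has gone tests whether that barrier has gone. Counting distant sites is a design choice.

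Third, a reader might set the ceiling against the 82%, 84% and 91% in sections 3.2 and 3.5 and conclude that the trial cannot match them. The plan makes no such comparison, any share is assumed, and the ceiling shown needs the all-treated denominator that section 10.0 contradicts. With surgery-only selection, even the direction of the net bias is not established.

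Fourth, 32 of 38 (84%) in section 3.2 is a mastectomy count in patients without distant metastases at diagnosis. A broader event is less directly comparable with it.

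These points limit the size and shape the remedy. They leave two gaps: a resection that cannot be credited under either denominator, and a scoring condition that rests on an optional scan.

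**Conclusion.** The point holds in limited form. Under 11.6.2, a patient without a breast cannot be scored as converted even when her inoperable recurrence is resected, and section 10.0's denominator does not rescue her. A compliant second-route patient may lack the reading on which her score depends, with no rule for that case. The mastectomy gap assumes that some enrolled recurrences follow mastectomy; the PET gap assumes that some second-route patients have ultrasound only. Both are plausible, but neither is quantified in the documents, so the 70% to 90% ceilings are illustrations.

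The endpoint is secondary and descriptive. The 60 patients, the stopping boundaries in 11.3.1 and the RECIST rule in 11.6.1 are not driven by it. A reader might infer otherwise from the statement in 11.6.2 that non-converters enter the primary efficacy analysis as non-responders. That sentence stands in the pCR paragraph and is a separate ambiguity; 11.6.1 does not use conversion. The correction should be made, but it does not threaten the trial's main conclusion.

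**What to change.** 1. In 11.6.2, define the qualifying event as resection of the locoregional gross disease (breast, chest wall or nodes) in a patient judged inoperable or questionably inoperable at entry. Keep the first route's objective-response condition and its credit for an operation offered and refused. Report the mastectomy-only rate alongside, for comparison with earlier series.
2. Reconcile 6.0 with 11.6.2. Either base second-route scoring on imaging that the protocol requires, using the PET/CT option already allowed at the first follow-up, or state how a second-route patient without PET is scored.
3. State one denominator for conversion in sections 1.0, 10.0 and 11.6.2. Patients inoperable or questionably inoperable at entry, including those considered inoperable under the second route, are the group that can convert.
4. Say whether distant FDG-avid disease is meant to veto conversion in M1 patients, and which route applies when a patient fits both. Report locoregional and distant FDG status separately.

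The cost is mainly wording, with no new visit and no new type of procedure. If the PET/CT option is chosen in item 2, a scan that is now optional becomes required for one subgroup. The broader event loses some comparability with the 32/38 series, which the mastectomy-only rate preserves.
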